## STAGE 2:

The analyses conducted in Stage 2 will be the exact same as in Stage 1, except the 10 mg and 50 mg dose of study drug will be replaced with a 100 mg dose of study drug. A separate and distinct placebo group will be used for Stage 2. The Hochberg procedure will have to address only two multiple comparisons, i.e., the MMRM slope models and the MMRM means models as there is now only one dose level comparison to placebo. The two alpha levels that may be needed to assess significance will be only  $\alpha_0=0.10$  and possibly  $\alpha_1=0.05$ . Here is the appropriate code for the LSESTIMATE statement.

LSESTIMATE tx\*week '100MG VS Placebo at Week 6' [1,100 6] [-1, P 6];

Also, as a reminder, the SAS code shown for the primary analysis can be used in this second stage as well for its primary analysis of hot flash frequency as well as for all secondary hot flash related endpoints.

## 6.3.1.1.1 Additional frequency analyses

The t-test or the or the Wilcoxon rank-sum test, if the data are determined to be non-normally distributed, will be used for between group treatment comparisons comparing the percentage change from baseline in the placebo arm to the percentage change from baseline in each treatment group (10 mg and 50 mg) at Day 42. The paired t-test or the Wilcoxon signed-rank test, if the data are determined to be non-normally

distributed, will be used for comparing baseline and Day 42 within each treatment group. The comparisons are as follows:

- Stage 1: Change from Baseline week to Week 6 between placebo and each of the 10 mg and 50 mg arms
- Stage 2: Change from Baseline week to Week 6 between placebo and the 100 mg
- Stage 1: Baseline week versus Week 6 for each treatment arm (placebo, 10 mg, and 50 mg)
- Stage 2: Baseline week versus Week 6 for each treatment arm (placebo and 100 mg)

# 6.3.1.1.2 Additional frequency analyses – sensitivity analyses among the ITT population Sensitivity analyses will also be conducted on the ITT population as described above.

## 6.3.1.1.1 Additional frequency analyses – sensitivity analyses including all severity levels

Sensitivity analyses on the percentage change in frequency of hot flashes from baseline to Week 6 will be conducted where a subject's frequency of hot flashes for a given week will include any hot flash designated as mild, moderate, or severe. This will be conducted among subjects in the EEIA population and among those in the ITT population.

## 6.3.2 Secondary Efficacy Variables

As noted previously, the same MMRM models - one for means and one for slopes - specified for the primary analysis will be used for each of the following hot flash related secondary endpoints including both frequency of hot flashes and severity of hot flashes.

#### 6.3.2.1 Percentage Change in severity of moderate and severe hot flashes from baseline to week 6

Analyzed with the same methods and considerations as for the analysis of frequency at week 6 (primary endpoint). Please see the data handling description (Section 6.3.1) for the specifics of severity calculation Repeat for Stage 2 as necessary.

## 6.3.2.2 Percentage Change in frequency of moderate and severe hot flashes from baseline to week 8

Analyzed with the same methods and considerations as for the analysis of frequency at week 6 (primary endpoint). Repeat for Stage 2 as necessary.

## 6.3.2.3 Percentage Change in frequency of moderate and severe hot flashes from baseline to week 10

Analyzed with the same methods and considerations as for the analysis of frequency at week 6 (primary endpoint). Repeat for Stage 2 as necessary.

#### 6.3.2.4 Percentage Change in frequency of moderate and severe hot flashes from baseline to week 12

Analyzed with the same methods and considerations as for the analysis of frequency at week 6 (primary endpoint). Repeat for Stage 2 as necessary.

#### 6.3.2.5 Percentage Change in severity of moderate and severe hot flashes from baseline to week 8

Analyzed with the same methods and considerations as for the analysis of frequency at week 6 (primary endpoint). Please see the data handling description (Section 6.3.1) for the specifics of severity calculation Repeat for Stage 2 as necessary.

## 6.3.2.6 Percentage Change in severity of moderate and severe hot flashes from baseline to week 10

Analyzed with the same methods and considerations as for the analysis of frequency at week 6 (primary endpoint). Please see the data handling description (Section 6.3.1) for the specifics of severity calculation Repeat for Stage 2 as necessary.

#### 6.3.2.7 Percentage Change in severity of moderate and severe hot flashes from baseline to week 12

Analyzed with the same methods and considerations as for the analysis of frequency at week 6 (primary endpoint). Please see the data handling description (Section 6.3.1) for the specifics of severity calculation Repeat for Stage 2 as necessary.

## 6.3.2.8 Percentage Change in frequency of moderate and severe hot flashes from baseline to week 4

Analyzed with the same methods and considerations as for the analysis of frequency at week 6 (primary endpoint). Repeat for Stage 2 as necessary.

## 6.3.2.9 Percentage Change in severity of moderate and severe hot flashes from baseline to week 4

Analyzed with the same methods and considerations as for the analysis of frequency at week 6 (primary endpoint). Please see the data handling description (Section 6.3.1) for the specifics of severity calculation Repeat for Stage 2 as necessary.

#### 6.3.2.10 Bone Marker Turnovers

## STAGE 1:

The secondary efficacy endpoint for bone marker turnovers is percentage change in bone turnover marker concentrations at Day 84 compared with baseline (Day 1, pre-dose). The bone markers to be assessed will include: serum C-telopeptide and bone specific alkaline phosphatase. For each marker, the mean, SD, median, minimum, and maximum will be summarized at each time point by treatment. The percentage change from baseline to Day 84 will also be summarized.

The t-test or the Wilcoxon rank-sum test, if the data are determined to be non-normally distributed, will be used for between group treatment comparisons comparing the percentage change from baseline in the placebo arm to the percentage change from baseline in each treatment group (10 mg and 50 mg) at Day 84. The paired T-test or the Wilcoxon signed-rank test, if the data are determined to be non-normally distributed, will be used for comparing baseline and Day 84 within each treatment group. Analyses will be conducted on the ITT population.

#### STAGE 2:

The same methods and analyses described directly above for Stage 1, will be repeated in Stage 2 for the placebo and 100 mg dose.

## 6.3.3 Exploratory Analysis

## 6.3.3.1 Change in Serum PSA Concentrations

#### STAGE 1:

A percentage change in serum PSA concentrations comparing baseline (Day 1, pre-dose) and each scheduled assessment (Days 30, 60, and 84) will be reported for each treatment group. The mean, SD, median, minimum, and maximum will be summarized at each time point by treatment. The percentage change from baseline to each scheduled assessment will also be summarized.

The t-test or the or the Wilcoxon rank-sum test, if the data are determined to be non-normally distributed, will be used for between group treatment comparisons comparing the percentage change from baseline in the placebo arm to the percentage change from baseline in each treatment group (10 mg and 50 mg) at Days 30, 60, and 84. The paired t-test or the Wilcoxon signed-rank test, if the data are determined to be non-normally distributed, will be used for comparing baseline and Day 84 within each treatment group. Analyses will be conducted on the ITT population.

## STAGE 2:

The same methods and analyses described directly above for Stage 1, will be repeated in Stage 2 for the placebo and 100 mg dose.

## 6.3.3.2 Change in Serum Total Testosterone and Serum Free Testosterone Concentrations

## STAGE 1:

A percentage change in serum total testosterone concentrations comparing baseline (Day 1, pre-dose) and each scheduled assessment (Days 30, 60, and 84) will be reported for each treatment group. The mean, SD, median, minimum, and maximum will be summarized at each time point by treatment. The percentage change from baseline to each scheduled assessment will also be summarized.

The t-test or the or the Wilcoxon rank-sum test, if the data are determined to be non-normally distributed, will be used for between group treatment comparisons comparing the percentage change from baseline in the placebo arm to the percentage change from baseline in each treatment group (10 mg and 50 mg) at Days 30, 60, and 84. The paired t-test or the Wilcoxon signed-rank test, if the data are determined to be non-normally distributed, will be used for comparing baseline and Day 84 within each treatment group. Analyses will be conducted on the ITT population.

Similar analyses will be implemented for serum free testosterone concentrations.

## STAGE 2:

The same methods and analyses described directly above for Stage 1, will be repeated in Stage 2 for the placebo and 100 mg dose.

## 6.3.3.3 Change in Serum SHBG Concentrations

#### STAGE 1:

A percentage change in serum SHBG concentrations comparing baseline (Day 1, pre-dose) and each scheduled assessment (Days 30, 60, and 84) will be reported for each treatment group. The mean, SD, median, minimum, and maximum will be summarized at each time point by treatment. The percentage change from baseline to each scheduled assessment will also be summarized.

The t-test or the or the Wilcoxon rank-sum test, if the data are determined to be non-normally distributed, will be used for between group treatment comparisons comparing the percentage change from baseline in the placebo arm to the percentage change from baseline in each treatment group (10 mg and 50 mg) at Days 30, 60, and 84. The paired t-test or the Wilcoxon signed-rank test, if the data are determined to be non-normally distributed, will be used for comparing baseline and Day 84 within each treatment group. Analyses will be conducted on the ITT population.

STAGE 2:

The same methods and analyses described directly above for Stage 1, will be repeated in Stage 2 for the placebo and 100 mg dose.

## 6.4 Safety Analysis

## 6.4.1 Adverse Events

A treatment-emergent adverse event (TEAE) is defined as any event not present before the date of treatment with the first dose of study drug, or any event already present that worsens in severity on or after the date of the first dose of study drug.

The calendar date is to be collected for the start and stop of each AE. In the event that only a partial end date (month/year) is available, and the month/year occurs before Day 1 in the treatment period of the study, the AE will not be considered treatment-emergent. However, if the onset date is a partial date (month/year) and the month/year occurs on or after Day 1 in the treatment period of the study, the following cases will be considered:

- The AE will be considered as treatment-emergent if:
  - The month/year of the onset date is later than the month/year of Day 1 in the treatment period.
  - The month/year of the onset date is equal to the month/year of Day 1 in the treatment period of study, and the AE is ongoing at the end of study or the end date and time are present in full or are partially provided such that they place the stop of the AE after the start of exposure to study treatment on Day 1 in the treatment period of the study.

Otherwise, the AE will be considered to be not treatment-emergent and will not be summarized; however, it will be included in the listing.

AEs will be summarized based on subjects having at least 1 occurrence of the AE at the level of the MedDRA preferred term, with the subject as the unit of analysis. If a subject has more than 1 AE of the same preferred term and there are different grades of severity, only the highest grade will be represented in the summary of severity. If the severity assessment is missing, the severity will be reported as 'unknown', and the known severity will be reported over the unknown severity. Each AE will be assessed for relatedness to the study treatment. If a subject has more than 1 AE of the same preferred term and there are different levels of relatedness to study treatment, only the highest level of relatedness for each will be represented in the summary of relatedness. Missing relationships will be included as related.

The following summaries of TEAEs by system organ class (SOC) and preferred term (PT) for the safety population will be provided. Summaries will be displayed by number of subjects with the event, percentage of subjects with the event and number of events reported by treatment group and overall for the following groups:

- TEAEs
- Serious adverse events (SAEs)

Similarly, summaries will also be displayed by number and percentage of subjects with the event reported by treatment group and overall for the following groups:

- TEAEs by maximum severity and incidence
- TEAEs by strongest relationship to study treatment number and incidence

Any adverse events, serious adverse events, actions taken due to adverse events, discontinuation from the study due to adverse events, adverse event outcomes, and adverse events resulting in study discontinuation will be listed.

Summary tables and listings will be presented by treatment group for the safety population.

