### **8.13 Adverse Events**

An adverse event (AE) is any unfavorable or unintended change in body structure (signs) or body function (symptoms), abnormal laboratory result that is associated with symptoms or requires treatment, or worsening of a pre-existing condition. This includes all such events regardless of the presumed relationship between the event and the study medication(s).

Any AE that occurs after the informed consent is signed but prior to dosing on Day 1 will be captured as part of the medical history and will be documented on the appropriate eCRF. This would include AEs resulting from concurrent illnesses, reactions to concomitant medications or progressive disease states. These AEs will be captured as part of the medical history.

Each subject will be assessed for the development of any adverse events. Adverse events should be assessed at each visit to the clinic. This information should be obtained in the form of non-leading questions (e.g., "How are you feeling?") and from signs and symptoms detected during each examination, observations of the study personnel or spontaneous reports from the subjects.

Any AEs such as complaints, signs, or symptoms that occur during the course of the study or designated follow-up periods will be recorded on the subject's case report form (eCRF). This would include AEs resulting from concurrent illnesses, reactions to concomitant medications, or progressive disease states.

Whenever possible, the AE will be described on the case report form using standard medical terminology consistent with Common Terminology Criteria for Adverse Events (CTCAE) version 4 in order to avoid the use of vague, ambiguous or colloquial expressions. The investigator will evaluate all adverse events as to their intensity, relation to test medication, outcome and action taken.

Each AE will be evaluated for duration, intensity, and relationship to (or association with) the study treatment (or other causes). Additionally, the actions taken (e.g., reduction of dosage, discontinuation of study medication, administration of treatment, etc.) and the resulting outcome of the AE will be indicated on the case report form.

Any subject who is withdrawn from the study due to an adverse event will be followed until the outcome of the event is determined, and the investigator will prepare a written summary of the event and document the available follow-up information on the case report form.

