## 6.2.5 Prior and Concomitant Medications and Therapies

The start and stop of each medication will be recorded by calendar date. "Prior medications" are defined as medications that have been discontinued prior to the date of first dose of study drug. "Concomitant medications" are defined as medications taken any day from the first dose of study drug until the last dose of study drug, regardless of whether the medication was initiated prior to the first dose of study drug.

The counts and percentages of subjects who took prior and concomitant medications will be summarized on the safety population, by treatment group and overall. Prior and concomitant medications will also be presented in subject data listings.

For partial start or stop dates, the following considerations and imputations will be performed.

- For a partial or missing start date where the stop date is recorded in full and is before the date of initial study treatment, it will be considered a prior medication. If the stop date is after the date of initial study treatment, it will be considered a concomitant medication.
- For a partial or missing stop date where the start date is recorded in full and the start date is after the initial study treatment date, it will be considered a concomitant medication.
- For instances where a medication has a partial stop date and a partial start date, the month and year of the stop date will be used to assess whether the medication is prior or concomitant. For instance, if month and year exist for the stop date, this data will be compared with the date of initial study treatment and if the month or year show evidence of being after this date or on the same date (same month/year), the medication will be considered concomitant.
- For medications where both the start and stop dates are missing, these medications will be considered concomitant.

The prior and concomitant medications taken during the study will be summarized using number of subjects (n) and percentage (%) in the safety population. All prior and concomitant medications will be coded using the WHODDE, version September 2015 or later, and then further coded against the

Anatomic Therapeutic Chemical (ATC) classification. Prior and concomitant medication data will be presented by ATC Level 2 and preferred term and will be presented by treatment group.

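### SAP 6.4.1 leaves some incompletely dated adverse events from the Day 1 calendar month out of the tables, and leaves missing or year-only onsets excluded or without a rule

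*SAP*

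**What the plan says.** SAP 6.4.1 defines a treatment-emergent event as "any event not present before the date of treatment with the first dose of study drug", or one already present that worsens from first dose onwards. It then deals with incomplete dates. The paragraph on onset applies "if the onset date is a partial date (month/year) and the month/year occurs on or after Day 1 in the treatment period", and gives two routes to treatment-emergent status:

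- "The month/year of the onset date is later than the month/year of Day 1 in the treatment period". No end date is needed.
- "The month/year of the onset date is equal to the month/year of Day 1", and in addition the event is ongoing at the end of study or its end date, full or partial, places its stop after first exposure.

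The paragraph closes with the default: "Otherwise, the AE will be considered to be not treatment-emergent and will not be summarized". The event stays in the listing. The summary tables that follow in the same section, including the one for serious events, are built from treatment-emergent events.

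Protocol 8.13 says that an event after consent but "prior to dosing on Day 1 will be captured as part of the medical history". Protocol 8.13.4 starts collection of serious events at first dose.

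Two other SAP defaults for missing information go the other way. On causality, SAP 6.4.1 says: "Missing relationships will be included as related". On drugs, SAP 6.2.5 says: "For medications where both the start and stop dates are missing, these medications will be considered concomitant".

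**The concern.** When timing is unclear, the default decides whether an event is counted as a possible harm. Here it decides against counting, although the protocol's recording rules make it likely that an event on the adverse event form began after dosing. None of the date patterns at issue shows that the event was present before first dose, so leaving them out also sits badly with the SAP's own definition.

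The error can run only one way. It falls on short or poorly dated events in the calendar month of Day 1, which usually contains the loading doses of Days 1-4. Safety and tolerability is a stated objective (Protocol 4.4, SAP 2.4), and the arms are small. The SAP takes the inclusive side for missing causality and for undated drugs, and gives no reason to treat event timing differently.

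**Working it through.** The documents give no figure to reproduce. The check is to run the rule over the possible date patterns and then to bound the size.

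**1. Date patterns.** Five onset states are crossed with five end states, 25 in all. The end states are: ongoing; full date after Day 1; month after the Day 1 month; same month as Day 1; missing and not ongoing. Year-only here means a year that does not itself place the onset before Day 1. TE means treatment-emergent.

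| Onset | Default read as general | Default limited to month-and-year onsets |
|---|---|---|
| Full date, on or after Day 1 | 5 TE | 5 TE |
| Month after the Day 1 month | 5 TE | 5 TE |
| Same month as Day 1 | 3 TE, 2 excluded | 3 TE, 2 excluded |
| Year only | 5 excluded | 5 with no rule |
| Missing | 5 excluded | 5 with no rule |
| Total | 13 TE, 12 excluded | 13 TE, 2 excluded, 10 with no rule |

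The two patterns excluded on either reading are an onset in the Day 1 month with (a) the end missing and the event not ongoing, or (b) the end known only as that same month. For example, if Day 1 is the 2nd of a month, a brief event dated only to that month is left out, although nearly all of the month is on treatment.

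On the general reading, a missing or year-only onset is excluded even if the event is ongoing or has a full end date after Day 1.

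**2. Which side the default should take.** Protocol 8.13 and 8.13.4 place pre-dose events outside the adverse event record. None of the 12 patterns shows a pre-dose onset, so all 12 would count if the default were reversed.

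**3. Size.** The documents give neither the number of events nor the share with incomplete dates. Assume two events per man and 1-3% with incomplete onset dates.

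- Stage 1 events: 90 x 2 = 180.
- Incomplete onset dates: 180 x 0.01 = 1.8, to 180 x 0.03 = 5.4.
- These are a ceiling. They are reached only if every incomplete date is missing, year-only or an unrescued same-month date, and the default is general.
- If all are month-and-year onsets spread evenly over 84 + 30 = 114 days, and on average about 15 days of the Day 1 month remain, the share in that month is 15/114 = 13%. The result is 1.8 x 0.13 = 0.2, to 5.4 x 0.13 = 0.7 events, before removing those kept by their end date. Early clustering of events would raise this.

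**4. Weight of one man.** 1/30 = 3.3 percentage points at the planned arm size (Protocol 6.1), or 1/40 = 2.5 points at the maximum of 40 per arm (Protocol 9.1).

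**The case against.** The best case against is that the gap is narrow and well guarded.

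- **Scope of the default.** It closes a paragraph about month-and-year onsets. Read in place, it does not reach missing or year-only onsets, which fall back on the general definition. This stands in part: for those dates the defect may be silence, not exclusion. The two same-month patterns are excluded either way.
- **Recording rules.** Events ongoing on Day 1 are recorded at that visit (Protocol 8.4, SAP 4.3), and Protocol 9.3.4 allows for events present when treatment starts. A few pre-dose events may therefore reach the form. This stands as a small exception, and weakens the presumption without reversing it.
- **Safeguards.** Start and stop dates are collected for each event, missing data are queried (Protocol 10.5.4), a Day 14 visit asks about events (Protocol 8.5), and the listing keeps every event. This stands, and is the main reason to expect few cases.

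Three stronger readings are tempting, and the documents do not support them:

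- A reader might infer that any event lacking an onset or an end date is dropped. A missing end date excludes nothing when the onset is complete and on treatment, or falls in a later month.
- A reader might take every incompletely dated event as lost, about 2 to 5 in Stage 1 on the assumptions above. The rule keeps later-month onsets, and same-month onsets that are ongoing or end later.
- A reader might infer that the loss would distort the decision on Stage 2. That decision uses a blinded safety review (Protocol 2.0, SAP 6.7), not arm-level tables, and a Safety Review Team reviews serious events throughout (SAP 6.8).

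**Conclusion.** The rule is wrong as written, and the severity is minor. Two same-month patterns are certainly excluded from the tables. Missing and year-only onsets are either excluded or have no rule, and both outcomes need repair. The direction is towards under-counting, against the protocol's recording rules and the SAP's other defaults.

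The number affected is unknown and probably small: from less than one event to a few in Stage 1, depending on the assumed event rate, the share of incomplete dates and their pattern. The conclusion that the default points the wrong way does not depend on those assumptions. It rests on the text of the rule and on adverse event records being mostly post-dose.

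**What to change.** Reverse the default in SAP 6.4.1 with one sentence that covers every kind of incomplete onset: an adverse event with a missing or incomplete onset date is treatment-emergent unless the known parts of its onset or end date show that it ended before first dose, or that it began before first dose and did not worsen afterwards.

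The cost is that sentence and the matching program logic. Event counts may rise slightly, and an occasional pre-dose event may be counted. To limit the latter, reconcile the Day 1 item on ongoing events (Protocol 8.4, SAP 4.3) with the medical history rule in Protocol 8.13, so that it is clear on which form such events belong.
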